### 3 STUDY ENROLLMENT AND WITHDRAWAL

#### 3.1 STUDY POPULATION

The study will enroll male and female adult subjects requesting fractional radiofrequency treatment of stretch marks until 15 subjects have been treated according to the study protocol.

#### 3.2 PARTICIPANT INCLUSION CRITERIA

1. Healthy, male or female subjects, 18-60 years of age who are seeking treatment for their stretch marks
2. Fitzpatrick skin type I-IV
3. Able to read, understand and voluntarily provide written Informed Consent.
4. Able and willing to comply with the treatment/follow-up schedule and requirements.

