### **2 STUDY DESIGN AND ENDPOINTS**

#### **2.1 DESCRIPTION OF THE STUDY DESIGN**

This is a prospective, single centre, evaluator-blind study of the performance of fractional radiofrequency (RF) for the treatment and revision of stretch marks.

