##### **2.1.1 PRIMARY ENDPOINT**

- Objective volumetric evaluation of striae via Antera 3D Imaging System Analysis at 12 and 16 weeks post-final treatment
- Improvement in the appearance of stretch marks at 12 weeks and 16 weeks post-treatment compared to baseline as assessed by investigator and blinded evaluators by photographic assessment utilizing the Global Aesthetic Improvement Scale (GAIS)

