#### 3.3 PARTICIPANT EXCLUSION CRITERIA

1. Pacemaker or internal defibrillator, or any other active electrical implant anywhere in the body (e.g. cochlear implant).
2. Subjects with any implantable metal device in the treatment area
3. Permanent implant in the treated area, such as metal plates and screws (excluding dental implants), or an injected chemical substance.
4. Current or history of any kind of cancer, or dysplastic nevi in the treated area.
5. Severe concurrent conditions, such as cardiac disorders.
6. Impaired immune system due to immunosuppressive diseases, such as AIDS and HIV, or use of immunosuppressive medications.
7. History of diseases stimulated by heat, such as recurrent herpes simplex in the treatment area; may be enrolled only following a prophylactic regime.
8. Poorly controlled endocrine disorders, such as diabetes.
9. Any active condition in the treatment area, such as sores, psoriasis, eczema, and rash.
10. History of skin disorders, such as keloids, abnormal wound healing, as well as very dry and fragile skin.
11. History of bleeding coagulopathies, or use of anticoagulants.
12. Use of isotretinoin (Accutane®) or other systemic retinoids limited up to 10mg/day or as per investigators discretion.
13. Treating over tattoo or permanent makeup.
14. Excessively tanned skin from sun, tanning beds or tanning creams within the last two weeks.

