### **4.3.3 FOLLOW-UP**

#### **Visit 6 – 12 Week Follow Up Post Final Treatment (+/- 7 days)**

Subjects will return to the clinic 12 weeks after the final treatment. Adverse events, and any changes to concomitant medications will be recorded. Subjects will complete a Patient Satisfaction questionnaire. Investigator to complete a Global Aesthetic Improvement Scale (GAIS) and Modified MSS assessment. Photographs of the treated area will be taken.

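### With no control described, the protocol neither restricts nor asks about other treatment of the assessed stretch marks, so its effect could be counted as device performance

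*Protocol*

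**What the plan says.** Protocol 2.1 describes the design: "This is a prospective, single centre, evaluator-blind study of the performance of fractional radiofrequency (RF) for the treatment and revision of stretch marks". No randomisation, control group or untreated comparison area is described. The heading of 4.1 contains the word control, but no control follows.

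The first primary endpoint (2.1.1) is "Objective volumetric evaluation of striae via Antera 3D Imaging System Analysis at 12 and 16 weeks post-final treatment", with no comparator named. The second is GAIS: "Improvement in the appearance of stretch marks at 12 weeks and 16 weeks post-treatment compared to baseline as assessed by investigator and blinded evaluators". MSS, a secondary endpoint (2.1.2), is also stated against baseline.

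Enrolment continues "until 15 subjects have been treated according to the study protocol" (3.1). Inclusion criterion 1 takes healthy adults "who are seeking treatment for their stretch marks". Inclusion criterion 4 asks that they be "Able and willing to comply with the treatment/follow-up schedule and requirements", but no requirement to abstain from other striae treatment is stated.

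Of the 14 exclusions in 3.3, the nearest is number 12: "Use of isotretinoin (Accutane®) or other systemic retinoids limited up to 10mg/day or as per investigators discretion". It concerns systemic drugs. Number 3 covers permanent implants and injected substances in the treated area. Number 14 covers tanning and is the only criterion with a time window.

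Concomitant medications are noted at the treatment visits. At both follow-up visits, "any changes to concomitant medications will be recorded". Procedures and cosmetic products are not mentioned.

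**The concern.** In an uncontrolled before-after comparison, whatever changes the assessed skin between baseline and follow-up enters the result. Here the subjects have come because they want their stretch marks treated, and they are followed for more than six months. Before the first endpoint visit there are 12 weeks with no scheduled contact. A subject who adds laser, needling or a topical product to the same area breaks no rule in the protocol, and nothing prompts the site to ask.

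Blinding the photographic evaluators guards against biased reading. It does not help here, because another treatment changes the skin being photographed. The same holds for the Antera measurement. Nor can a later analysis plan repair this: it cannot set aside assessments affected by procedures or cosmetics that were never recorded.

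**Working it through.** **1. Is there a rule anywhere?** The sections of the protocol that could hold one compare as follows.

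| Section | Content nearest to the point | Covers other striae treatment? |
|---|---|---|
| 3.2, 4 inclusion criteria | Seeking treatment; willing to comply | No |
| 3.3, 14 exclusion criteria | Systemic retinoids; implants or injected substances; recent tanning | Only in part, through drugs or substances named for themselves |
| 3.4.1, withdrawal | Medical reasons; an exclusion criterion newly met | No; there is no such criterion to meet |
| 4.1.2, device | Settings, spacing, area size | No |
| 4.3.1, screening | Medical and surgical history reviewed | History taken, no rule attached |
| 4.3.2 and 4.3.3, Visits 2 to 7 | Concomitant medications recorded | Drugs recorded, not restricted; procedures and cosmetics absent |

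**2. How long is the exposure?** Treatment 4 is at week 12 and Visit 7 is 16 weeks later: 12 + 16 = 28 weeks. At the longest spacing in 4.1.2 (three gaps of 6 weeks) it is 18 + 16 = 34 weeks.

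**3. What does one subject do to the result?** Suppose GAIS is summarised as the proportion improved (an assumption; the protocol names no summary). With n = 15, each subject whose improvement comes from another treatment moves that proportion by 1/15 = 6.7 points. Two subjects move it by 2/15 = 13.3 points and three by 3/15 = 20.0 points.

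**4. How likely is some use?** The documents give no rate q, so a range is assumed. P(at least one of 15) = 1 − (1 − q)^15.

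| Assumed rate of use | At least one user | At least two users |
|---|---|---|
| 5% | 0.54 | 0.17 |
| 10% | 0.79 | 0.45 |
| 20% | 0.97 | 0.83 |
| 30% | above 0.99 | 0.97 |

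**5. What does it do to a test?** The protocol names no test, significance level or SD. As an illustration, take a continuous change score with no device effect, n = 15, and a two-sided 5% one-sample t-test. If m users are each shifted by d SD, the mean shifts by m × d / 15 SD, which is m × d / √15 standard errors. For m = 3 and d = 1 this is 0.20 SD, or 0.77 standard errors. For m = 5 and d = 1 it is 0.33 SD, or 1.29 standard errors. Simulated rejection rates, against 5% nominal:

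| Users among 15 | d = 0.25 SD | d = 0.5 SD | d = 1 SD |
|---|---|---|---|
| 3 | about 5% | about 6% | about 8.5% |
| 5 | not shown | about 8% | about 17% |

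One user at 1 SD leaves the rate at about 5%, and two give about 6%. Both m and d are assumptions.

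**The case against.** The strongest reply is that this argues from silence. No sentence of the protocol is wrong, and some of the text is not available: a Schedule of Events table is referred to but not shown, the numbering skips 4.1.1 and 4.2, and consent pages were removed. A rule could sit there. This limits certainty. Even so, eligibility criteria and visit procedures are where such a rule belongs, and those sections are shown and contain none.

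The second reply is that handling such use in the analysis belongs to the statistical analysis plan. That is true of the estimand detail. It is not true of whether use is restricted or asked about.

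Several stronger readings are tempting, and the documents do not support them:

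- A reader might infer that another treatment's effect is in fact credited to the device. Nothing shows that any subject uses one, and 3.1 describes subjects as requesting this particular treatment. The text supports only that it could happen.
- A reader might infer that all earlier treatment biases the result. An effect completed before baseline is already in the baseline value; only a continuing or delayed effect carries over.
- A reader might infer that every efficacy endpoint is a change from baseline. Only GAIS and MSS are stated so. The Antera endpoint names no comparator, and subject satisfaction is not a change score.
- A reader might infer that the exclusions serve safety alone. The protocol gives no reasons for them, and numbers 3 and 12 overlap in part with other treatment.
- A reader might infer that nothing would be traceable. Topical drugs may be captured as concomitant medications; the clearer gap is procedures and cosmetics.
- A reader might take 17% as the false-positive rate. That needs a third of subjects to use an effective co-treatment worth 1 SD, and a t-test fits a rating scale such as GAIS poorly.

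**Conclusion.** The point stands in this form: the eligibility and conduct rules as written leave other treatment of the assessed striae unrestricted and, apart from medications, unrecorded, in a study with no control described. Concurrent treatment is the main risk, with a continuing effect of recent earlier treatment second.

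The firmest measure of size is the 6.7 points that one subject in 15 contributes to a GAIS improvement rate. The test illustration runs from almost no effect to roughly a threefold rise in the rejection rate (17% against 5%), depending wholly on assumed use and effect. That the study is single-arm is itself an inference from the absence of any described comparator. The study can run without the change, but a claim that the observed improvement is due to the device would be exposed. The sponsor should make the change.

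**What to change.** - In 3.3, add an eligibility restriction on other treatment of the assessed striae. Its scope and any washout are for the sponsor and investigator to set.
- In 4.3, add the matching restriction on conduct during the study, on the same footing, and say what happens when it is breached.
- At every visit, ask about and record other treatment of the assessed area, covering procedures and cosmetic products as well as drugs, with dates.
- Report the primary endpoints with and without assessments made after such use. The detail can go in the statistical analysis plan.

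The cost is a sentence or two in each of 3.3 and 4.3, one question per visit and one sensitivity analysis. The downside is that a few candidates may be ineligible or delayed.

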#### 3.3 PARTICIPANT EXCLUSION CRITERIA

1. Pacemaker or internal defibrillator, or any other active electrical implant anywhere in the body (e.g. cochlear implant).
2. Subjects with any implantable metal device in the treatment area
3. Permanent implant in the treated area, such as metal plates and screws (excluding dental implants), or an injected chemical substance.
4. Current or history of any kind of cancer, or dysplastic nevi in the treated area.
5. Severe concurrent conditions, such as cardiac disorders.
6. Impaired immune system due to immunosuppressive diseases, such as AIDS and HIV, or use of immunosuppressive medications.
7. History of diseases stimulated by heat, such as recurrent herpes simplex in the treatment area; may be enrolled only following a prophylactic regime.
8. Poorly controlled endocrine disorders, such as diabetes.
9. Any active condition in the treatment area, such as sores, psoriasis, eczema, and rash.
10. History of skin disorders, such as keloids, abnormal wound healing, as well as very dry and fragile skin.
11. History of bleeding coagulopathies, or use of anticoagulants.
12. Use of isotretinoin (Accutane®) or other systemic retinoids limited up to 10mg/day or as per investigators discretion.
13. Treating over tattoo or permanent makeup.
14. Excessively tanned skin from sun, tanning beds or tanning creams within the last two weeks.

#### 3.4 PARTICIPANT WITHDRAWAL OR TERMINATION

##### 3.4.1 REASONS FOR WITHDRAWAL OR TERMINATION

Subjects are free to withdraw from participation in the study without prejudice at any time upon request.

The investigator may terminate participation in the study if:

- Any clinical adverse event (AE), laboratory abnormality, or other medical condition or situation occurs such that continued participation in the study would not be in the best interest of the subject.
- The subject meets an exclusion criterion (either newly developed or not previously recognized) that precludes further study participation.

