## 4 INVESTIGATIONAL DEVICE

### 4.1 INVESTIGATIONAL DEVICE AND CONTROL DESCRIPTION

#### 4.1.2 DEVICE SPECIFIC CONSIDERATIONS

- Device model(s): Venus Viva™
- Device settings and programming: Ablation or Coagulation Mode; 180-280 volts, 5-30 ms pulse duration
- Duration of exposure and frequency: Multiple passes, 4 treatments, roughly 4-6 weeks apart, multiple treatment areas per subject may be treated. Treatment area size – 3"x3" or smaller

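### Section 3.4.1 allows a subject to be taken out of the study, not only off treatment, for a reaction the device may have caused, and keeps no 12- or 16-week follow-up for that subject

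*Protocol*

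**What the plan says.** Protocol section 3.4.1 opens its list with "The investigator may terminate participation in the study if" and gives two grounds. The first begins "Any clinical adverse event (AE), laboratory abnormality, or other medical condition or situation occurs such that continued participation in the study would not be in" and turns on what is best for that person. The second is "The subject meets an exclusion criterion (either newly developed or not previously recognized) that precludes further study participation".

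Among the exclusion criteria in section 3.3, item 9 is "Any active condition in the treatment area, such as sores, psoriasis, eczema, and rash". Item 10 is "History of skin disorders, such as keloids, abnormal wound healing, as well as very dry and fragile skin".

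The device is used on that same skin in "Ablation or Coagulation Mode; 180-280 volts, 5-30 ms pulse duration", over four treatments (section 4.1.2). The first primary endpoint is "Objective volumetric evaluation of striae via Antera 3D Imaging System Analysis at 12 and 16 weeks post-final treatment". The second (GAIS) and both secondary performance endpoints (modified MSS and satisfaction) are read at the same two times. The safety endpoint counts treatment-related adverse events up to 16 weeks (section 2.1.3).

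Section 3.1 sets enrolment to run "until 15 subjects have been treated according to the study protocol". Section 4.3.3, under Visit 7, closes adverse event recording 7 days (non-serious) or 30 days (serious) after a subject's last day in the study.

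**The concern.** Both grounds end participation in the study. The protocol does not distinguish stopping the device from leaving follow-up, and it does not exempt conditions that the device may have produced. A subject with a bad local reaction can therefore leave before any performance endpoint is read, for a reason located in the skin to be scored.

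Loss of that kind is plausibly related to outcome. The study is small and the protocol describes no control group, so nothing would offset a favourable selection. An analysis plan can say how missing readings are handled, but it cannot recover readings that the protocol allowed to go uncollected. Safety is affected too, because a subject who leaves early is watched for less time than the safety endpoint requires.

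**Working it through.** The protocol gives no rate of improvement, skin reaction or withdrawal, so there is no figure to reproduce. The check is a reading of the text followed by illustrations on stated assumptions.

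**1. Can a device reaction meet the rule?** Section 3.4.1 extends the exclusion list to newly developed conditions. Item 9 is defined by site and by being active, with sores and rash as examples, and it does not mention cause. A sore or rash produced by the device in the treated area fits that wording. The adverse event ground reaches the same subject independently.

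**2. What is lost?** On the nominal schedule the last treatment is at week 12 (section 4.3.2). The readings fall at weeks 12 + 12 = 24 and 12 + 16 = 28. A subject removed during the treatment phase has neither.

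**3. What happens to safety recording?** Assume a subject has Treatment 1 on day 0 and leaves on day 28.
- Non-serious recording ends on day 28 + 7 = 35, and serious recording on day 28 + 30 = 58.
- Sixteen weeks after the only treatment received is day 16 × 7 = 112.
- The uncovered time is 112 − 35 = 77 days for non-serious events and 112 − 58 = 54 days for serious events.

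**4. How often could the rule come into play?** If each of 15 subjects has risk p of an active condition in the treated area, the chance of at least one is 1 − (1 − p)^15.

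| Assumed p | At least one of 15 |
|---|---|
| 5% | 53.7% |
| 10% | 79.4% |
| 20% | 96.5% |

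This is the chance that the ground becomes available, not that anyone is removed.

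**5. What could it do to an improvement rate?** Assume 10 of 15 improve (66.7%; exact 95% interval 38.4% to 88.2%) and all those removed are non-improvers.

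| Removed | Rate | Change |
|---|---|---|
| 1 | 10/14 = 71.4% | +4.8 points |
| 2 | 10/13 = 76.9% | +10.3 points |
| 3 | 10/12 = 83.3% | +16.7 points |

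With 8 to 11 improvers of 15, the rise runs from 8/14 − 8/15 = 3.8 points to 11/12 − 11/15 = 18.3 points.

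The direction depends on who leaves. If the 2 removed were improvers, the rate would be 8/13 = 61.5%, and removal unrelated to outcome leaves the expected rate unchanged.

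**6. Does replacement repair it?** If 2 removed non-improvers are replaced by subjects who improve at the rate seen in those retained, the expected rate is (10 + 2 × 10/13)/15 = 76.9%. The denominator returns to 15 and the shift stays, so the final count would not reveal it.

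**The case against.** The strongest reply is that section 3.4.1 is permissive and confined to a criterion that precludes further participation. Visits 6 and 7 involve no device treatment, only event and medication review, a questionnaire, scoring and photographs. A sensible investigator could find that a rash precludes none of this and keep the subject. That stands as a limit on the claim: removal is possible, not automatic. It does not close the gap, because the protocol never says which criteria preclude participation or that follow-up continues after treatment stops.

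Several stronger readings are tempting and are not supported:

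- A reader might infer that poor healing after treatment meets item 10. That item concerns history and is not restricted to the treated area. Item 9 carries the point alone.
- A reader might infer that harm disappears from the safety results. An event recorded before removal still counts towards the safety endpoint. What can be missed is what happens after the recording window closes.
- A reader might infer that the investigator who decides on removal also controls the result. Section 2.1.1 adds blinded evaluators for GAIS and an instrument-based volumetric measure. These protect the scoring of subjects who are present but cannot score those who are absent.
- A reader might think that narrowing the exclusion-criterion ground is enough. The same subject could still leave through the adverse event ground.

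It is also fair to say that the percentages are assumed, use a simple improved/not improved split that the protocol does not define, and do not bear on the volumetric endpoint. They show the mechanism only. How subjects without a reading are counted may be settled in an analysis plan that is not shown, and no criticism is made of that.

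**Conclusion.** The point holds as a gap in data collection. As written, section 3.4.1 permits loss from the study that is related to outcome, on either ground, and nothing preserves the 12- and 16-week readings or adverse event capture to 16 weeks for those subjects. Replacement, which section 3.1 implies but does not spell out, could hide the loss.

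The documents do not show that such removals will occur or how large any bias would be. On the assumption of 10 improvers in 15 and removals confined to non-improvers, the gain is about 5 to 17 points for 1 to 3 removals. It would be smaller, absent or reversed if removals were less closely tied to poor outcome. The change is worth making because it is cheap and because the lost readings cannot be recovered at analysis.

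**What to change.** Add to section 3.4.1, applying to both grounds:

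- Stopping treatment does not by itself end study participation.
- Every subject who received at least one treatment is asked to attend the 12- and 16-week visits, with all assessments and adverse event recording, unless consent is withdrawn. For subjects who stop early, state the date from which those weeks are counted.
- A condition that first arises in a treated area after Treatment 1 is recorded as an adverse event.
- All terminations and replacements are reported with their reasons.

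Section 3.1 should say whether a subject who stops early is replaced. Whether treatment continues remains a clinical decision, and nothing here changes it.

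The cost is a few sentences and some follow-up visits for subjects who would otherwise have left. The reported improvement rate may be slightly less favourable.

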### 3.4.2 PREMATURE TERMINATION OR SUSPENSION OF STUDY

The principal investigator or regulatory authority may suspend or prematurely terminate participation in the study at the investigation site for which they are responsible.

## 4 INVESTIGATIONAL DEVICE

### 4.1 INVESTIGATIONAL DEVICE AND CONTROL DESCRIPTION

#### 4.1.2 DEVICE SPECIFIC CONSIDERATIONS

- Device model(s): Venus Viva™
- Device settings and programming: Ablation or Coagulation Mode; 180-280 volts, 5-30 ms pulse duration
- Duration of exposure and frequency: Multiple passes, 4 treatments, roughly 4-6 weeks apart, multiple treatment areas per subject may be treated. Treatment area size – 3"x3" or smaller

## 4.3 STUDY SCHEDULE

### 4.3.1 SCREENING

#### **Visit 1, Screening Visit (Day -14 to 0)**

Informed consent will be obtained from the subject prior to any study procedure, clearly indicating his/her understanding of the requirements and possible risks associated with study participation and other applicable treatment options.

Subject will be screened for eligibility to participate in the clinical study using the inclusion/exclusion criteria. During screening, the study doctor will review the subject's medical/surgical history, demographics and examine the subject's targeted area to ensure that it meets the study criteria.

